At the time of writing, it is unclear what volume of patients have been referred to the CO@h pathway, and what onboarding data will be available due to pressure on the system to cope with the pandemic. As a result, the study may be underpowered. This risk is further exacerbated by the fact that the primary outcomes relate to use of critical care beds and mortality. The mixed-methods study of pilots of remote home monitoring models in England

found that for the pre-hospital model of CO@h, although 10% (174/1,737) of patients that were monitored deteriorated and were escalated, 0.2% (3/1,737) of patients were admitted to ICU and 1% (20/1,737) died.¹ See the Power calculation section for further details

All decisions taken after this statistical analysis protocol (SAP) has been finalised will be documented and justified in an addendum to it. We may run interim analyses on incomplete data to provide the CO@h programme team with some preliminary indications of results. The results of the final analysis will be published in line with the Health Foundation's Improvement Analytic Unit's (IAU's) aim of openness and transparency.

Study outcomes

We will analyse outcomes in the 28-day period following a COVID-19 positive test (ie equal to or less than 28 days from a positive test, with the date of the first COVID-positive test being equal to day zero). We are limiting most of the outcomes to binary variables (ie capturing whether there was an A&E attendance rather than the number of attendances); this is because of the short follow-up period and likely sparsity in hospital event counts other than 0 and 1 (which we will confirm on receipt of the data). The following outcomes will be included:

- Type 1 A&E attendance (binary outcome yes/no)
- Emergency admission (binary outcome yes/no)
- Critical care bed use (binary outcome yes/no)
 - This will capture a stay in ICU at any point during an admission, which could be as a result of either an emergency or an elective admission.
 - This variable includes level 2 and level 3 beds, as well as beds under code 5 (flexible critical care beds where there is a mix of level 2 and level 3 beds) and code 90 (temporary use of non-critical care beds).¹²
- Total emergency hospital bed days

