- **General Practice Extraction Service (GPES) Data for Pandemic Planning and Research (GDPPR)** – this data set comprises general practice data on patients registered in 97.5% of all practices in England.¹⁵ This will be the source of data on baseline characteristics for the patients included in our analysis. The age of patients (in whole weeks relative to a reference date) will be calculated by NHS Digital using this data set. From this, we will derive the age at first COVID-19 positive test (eg 65 years and 3 weeks). We will request data for patients born between 1 October 1940 (ie turning 80 on 1 October 2020, the earliest potential study start date) and 1 May 1971 (ie turning 50 on 1 May 2021).
- **Second Generation Surveillance System (SGSS)** – this system holds data on COVID-positive tests, including the full date of first COVID-positive test. SGSS is the national laboratory reporting system used in England to capture routine laboratory data (mainly on infectious diseases and antimicrobial resistance). Only the first COVID-positive test is captured in this database. We will also be provided testing data from the COVID-19 UK Non-hospital Testing Results ('pillar 2'). These sources will be used to identify our study cohort.
- **Shielded Patient List** – this data set identifies patients regarded as clinically extremely vulnerable (CEV) and at high risk of serious illness from COVID-19.
- **CO@h onboarding data** – this data set lists the date of patient onboarding (ie enrolment onto the CO@h intervention). These data will allow us to check the assumptions of a discontinuity in onboarding at age 65 and allow us to make use of a fuzzy RDD. In addition, by triangulating with hospital data, we will be able to check other assumptions – eg that onboarding is primarily occurring pre-hospital. Onboarding data were due to be collected across all CCGs from 1 December 2020, with the option of retrospectively collected data from as early as 1 October 2020 from sites that started rolling-out CO@h earlier. However, due to COVID-19 pressures, as of mid-January 2021 these patient-level data are not currently being reliably recorded nationally. Thus, the quality of this data set is a key risk to the execution and validity of the study and its ability to identify a treatment effect.

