- **CO@h offboarding data** – these data will be used to check that our proposed 28-day follow-up period adequately captures the duration of CO@h use (which is intended to usually last up to 14 days from first symptoms, according to the SOP). The various quality issues affecting the onboarding data also affect this data set.
- **Hospital Episode Statistics (HES)** – this data set will include information on hospital admissions and critical care spells.

* Although we will estimate the intervention effect at age 65, we will require data on either side of the threshold to do so. The range or window of ages required will be determined using data-driven methods, but it is expected that 50–79 will be a large enough range not to restrict this choice prematurely.

- **Emergency Care Data Set (ECDS)** – this will be used to provide information on A&E attendances.
- **Office for National Statistics (ONS) mortality data** – this data set will include the registered date of death of any patients that died during the study period.
- **Data used to flag care home residents** – based on patient registration information derived from pseudonymised National Health Application and Infrastructure Services (NHAIS) data.

We will also receive information from Kent, Surrey & Sussex Academic Health Science Network (AHSN) on when each CCG began to implement CO@h and when they were considered ‘fully operational’ (see the later section on Study period, index dates and follow-up period). We will also access publicly available data that maps GP practices to CCGs at the earliest date of study start.

If onboarding data are delayed or unavailable, we may receive aggregate data on number of onboarded patients by CCG. This would allow us to determine whether areas are implementing CO@h at a scale sufficient to potentially identify an effect based on a ‘sharp’ RDD, whereby a treatment assignment effect is estimated (see later section on Statistical methods for more detail).

Study cohort

The study cohort consists of patients in England with a first COVID-19 positive test that were aged 50–79 at the time of test, with the following patient-level and area-level exclusions.

Patient-level exclusions:

- Patients with unlinked records
- Patients who are not captured in the GDPDR
- Patients with missing age or sex information
- Patients onboarded onto CO@h who do not have a first COVID-positive test
- Patients who are CEV
- Potential additional exclusion: patients living in care homes

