As of 14 February 2021, there were 4,182 patients with COVID-19 symptoms within the last 14 days enrolled in the PRINCIPLE trial. We will attempt to source aggregate numbers of trial participants by age band and enrolment period, which should enable us to gauge the extent to which the two interventions are intertwined, but we would not be able to exclude trial participants, as this would introduce bias within the RDD. Therefore, we will examine the numbers of patients on PRINCIPLE and CO@h within the window of ages used in the analysis and aim to end the study period before an estimated 5% of patients in this range are likely to have been enrolled onto PRINCIPLE. This should limit the risk that these patients have a substantive effect on the outcomes of our evaluation. We may also vary the study period end date by area, depending on the roll-out of the PRINCIPLE trial, if data are available to assess this geographically. We will confirm the area-level study start and end dates and document them in an addendum to this SAP following receipt of relevant information and data.

Each patient is assigned an index date – the date of their first COVID-19 positive test – which determines the patient’s baseline and the start of their follow-up period. We will use the date of the first COVID-19 positive test rather than the date of onboarding because this allows consistent start dates for both patients who received the intervention and those who did not. This evaluation examines the effectiveness of CO@h during a 28-day period from this date, which is likely to include a period of time before patients had access to a pulse oximeter. This will allow us to evaluate the effectiveness of CO@h as it is used in practice, which may be dependent on whether pulse oximeters are distributed in time to support patients’ needs and care. We considered using the date of first onset of symptoms as the index date, as it is used by implementation teams to determine for how long oximeters should be used (ie 14 days from start of onset, unless there are signs of deterioration). However, this information is not routinely collected.

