In the current study, the sharp design estimates the average effect of CO@h on all patients who are eligible compared to all patients who are not (regardless of oximeter receipt and use). The fuzzy design will allow us to factor in treatment receipt: a proportion of patients aged 65 and over will not receive an oximeter and some patients aged under 65 will. In other words, compliance in the current study means that patients' receipt of oximeters aligns with their eligibility.

The fuzzy design can be used to estimate the average treatment effect for these 'complier' patients (within the window of ages used in the analysis) under certain assumptions: either (a) local independence between the treatment effect and compliance behaviour, or (b) a monotonicity condition. The monotonicity condition assumes that the 'compliance behaviour' for a patient (ie of being enrolled if they are aged 65 or over or not being enrolled if they are under 65) would be the same whether that patient was eligible or not, ie it is monotonic with respect to the running variable. This means that there are no 'local defiers', ie patients within the window around the threshold who are more likely to be enrolled in CO@h because they are below the age threshold (or vice versa).²¹

Assuming reliable patient-level onboarding data are available, we will aim to check how many patients are non-compliers due to incongruent oximeter receipt and make use of a fuzzy RDD in our main analysis. We will not have information on oximeter use by patients, and so this is not something we can analyse or incorporate in the RDD. The resulting average treatment effect estimates will relate only to compliers; the method does not allow any estimates to be made for the potential effect of the treatment on patients that would always either (a) receive the treatment, or (b) not receive the treatment, regardless of eligibility. (Note: CEV patients, who are expected to receive the intervention regardless of age, have been excluded from the analysis.)

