The null hypothesis for the Fisher-based simulation will assume complete randomisation of patients to treatment within the window. A confidence interval will be estimated for the treatment effect by inverting the calculation for the Fisher-based p-value and identifying values of treatment effect which are not significantly different to the estimated effect. As a comparison to the Fisher-based approach, we will also estimate the p-value using the large-sample Neyman approach based on normal approximation, and also report the power of the Neyman test to inform interpretation.¹⁷ If the results of the Fisher and Neyman approaches differ, we will consider the number of observations within the window to determine which approach is most valid, with the Fisher framework being preferred where sample sizes within the window are small.

Many of our outcomes are binary. In these cases, the estimated treatment effects will comprise differences in mean outcomes on the per cent scale. For our other outcomes, the treatment effects will be differences in mean bed days. As well as the treatment effects, we will also present the point estimates for the treated and control groups in each case. We will not control for the baseline variables in the model, as the window selection procedure will already have been used to identify groups which are comparable in terms of these variables.

Calculation of intervention estimates where outcomes happen before enrolment

This evaluation aims to estimate the effect of pre-hospitalisation CO@h, as detailed in the SOP.² Although we will exclude any CCGs which are identified as only offering enrolment in CO@h at hospital discharge, it is conceivable that other CCGs may offer a combination of pre-hospital and post-discharge as part of the CO@h model, especially in those areas that had implemented a post-discharge model early on in the pandemic. There may therefore be some patients enrolled in CO@h at hospital discharge that we can identify by triangulating date of onboarding with date of hospital discharge. These patients will be considered as not having received the CO@h intervention (ie treatment receipt = 0), similar to those patients enrolled in CVWs (for whom we do not have data).

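### Patients already admitted before their first positive test stay in the cohort: they do not bias the fuzzy estimate, but they cost precision on the rare primary outcomes

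*SAP*

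**What the plan says.** SAP, Study cohort: "The study cohort consists of patients in England with a first COVID-19 positive test", aged 50–79 at the test. The patient-level exclusions are unlinked records, absence from the GP data set, missing age or sex, onboarding without a positive test, CEV status, and finally "Potential additional exclusion: patients living in care homes". None concerns hospital status at the test. The area-level exclusions remove CCGs that only or mostly ran a step-down model, not individual inpatients.

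SAP, Sources of data: tests come from the national laboratory reporting system, and then "We will also be provided testing data from the COVID-19 UK Non-hospital Testing Results". Non-hospital results are an additional feed, so the laboratory feed is not presented as community-only.

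SAP, Study period, index dates and follow-up period: the index date is "the date of their first COVID-19 positive test". Outcomes run from that day (day 0) to day 28. For critical care, SAP, Study outcomes says: "This will capture a stay in ICU at any point during an admission". It does not require the admission to start after the test.

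SAP, Calculation of intervention estimates where outcomes happen before enrolment: "This evaluation aims to estimate the effect of pre-hospitalisation CO@h, as detailed in the SOP". For those enrolled at discharge, "These patients will be considered as not having received the CO@h intervention (ie treatment receipt = 0"). Patients enrolled through A&E have receipt set outcome by outcome. Both rules change how receipt is coded for people who are later onboarded. Neither removes anyone, and neither mentions inpatients who are never onboarded.

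SAP, Sharp and fuzzy designs: if onboarding data are reliable, the team will "make use of a fuzzy RDD in our main analysis". The sharp analysis is sensitivity analysis 1, and the fallback if onboarding data fail.

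**The concern.** The programme is meant to act before hospital. Someone already admitted when the first positive swab is taken is, with few exceptions, past that point. Such patients are likely to have much higher risks of critical care and death than people tested in the community. Even a small share of the cohort could therefore supply a large share of the primary events, on which pre-hospital monitoring can hardly act.

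The SAP warns more than once that the study may be underpowered for critical care and death. It does not name this source of lost precision, which can be removed with data already requested. The reference rates under Table 1 (0.2% ICU, 1% death) come from onboarded pre-hospital patients, so they do not describe a cohort that also contains inpatients.

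**Working it through.** **1. Reproducing the plan's figure.** Inputs from SAP, Power calculation: two-sided 5%, 80% power, equal groups, full compliance. With p̄ the mean of the two risks, the pooled-variance normal approximation gives per group

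n = [1.960·√(2p̄(1−p̄)) + 0.842·√(p₁(1−p₁) + p₂(1−p₂))]² / (p₁−p₂)².

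For 2% v 1.5%, n = 10,795 and N = 21,590, as in Table 1. All 21 cells of the table reproduce. Table 1 is not in error.

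**2. Effect on the estimates.** Let h be the inpatients' share of the cohort, equal on both sides of 65, and r their risk, unaffected by eligibility. Among the other patients let Δ be the difference in outcome at 65 and δ the jump in enrolment.

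- Intention-to-treat difference in the whole cohort: (1−h)Δ.
- Jump in enrolment in the whole cohort: (1−h)δ.
- Fuzzy (complier) effect: (1−h)Δ / (1−h)δ = Δ/δ, unchanged.

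The complier effect is not biased. The absolute intention-to-treat difference shrinks only by the factor 1−h.

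**3. Effect on precision, by share of events.** Let f be the share of control-group events that come from inpatients. The SAP does not give f, so 20%, 40% and 60% are assumptions. Take 2% v 1.5% in the remaining patients and h small enough that the difference stays at 0.5 points. The control risk is then 2%/(1−f), and the eligible risk is 0.5 points lower.

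| f | Control v eligible risk | Apparent relative risk | N | Ratio to 21,590 |
|---|---|---|---|---|
| 0 | 2.00% v 1.50% | 0.75 | 21,590 | 1 |
| 20% | 2.50% v 2.00% | 0.80 | 27,618 | 1.28 |
| 40% | 3.33% v 2.83% | 0.85 | 37,526 | 1.74 |
| 60% | 5.00% v 4.50% | 0.90 | 56,816 | 2.63 |

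The last row is itself a cell of Table 1 (5.0%, relative risk 90%).

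**4. The same check with explicit h and r.** Both are assumptions. Control risk = (1−h)p + hr; eligible risk = (1−h)p·RR + hr; RR = 0.75 in the remaining patients. Baselines p are the pilot rates quoted in the SAP.

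| Outcome | h, r | Control v eligible risk | Inpatient share of control events | N | Ratio |
|---|---|---|---|---|---|
| Death, 1% | none | 1.000% v 0.750% | 0 | 43,568 | 1 |
| Death, 1% | 2%, 10% | 1.180% v 0.935% | 17% | 54,726 | 1.26 |
| Death, 1% | 5%, 10% | 1.450% v 1.2125% | 34% | 73,110 | 1.68 |
| Death, 1% | 10%, 20% | 2.900% v 2.675% | 69% | 168,050 | 3.86 |
| ICU, 0.2% | none | 0.200% v 0.150% | 0 | 219,382 | 1 |
| ICU, 0.2% | 2%, 10% | 0.396% v 0.347% | 51% | 483,968 | 2.21 |
| ICU, 0.2% | 5%, 10% | 0.690% v 0.6425% | 72% | 920,902 | 4.20 |

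At h = 5%, r = 10%, the death difference moves only from 0.25 to 0.2375 points (0.25 × 0.95). Nearly all of the increase in N comes from added variance. All N assume full compliance, as Table 1 does, so the ratios matter more than the totals.

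**The case against.** **No validity error.** The main analysis is fuzzy, and the SAP already expects patients who would not receive CO@h whatever their age. SAP, Main analysis reports binary effects as absolute differences on the per cent scale. A reader might infer that inpatients seriously dilute or bias the intention-to-treat effect. The SAP does not support that: the absolute difference shrinks only by 1−h, and only a relative effect, which the SAP does not estimate, would move much. This objection stands. The loss of precision remains, in the fuzzy and the sharp analysis alike.

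**Exclusion may itself select on the intervention.** Eligibility allows onboarding on clinical diagnosis before any test, and earlier admission is part of the hypothesised mechanism. Someone aged 65 or over who was escalated by CO@h and first swabbed after admission would be removed because the programme had acted. This stands as a caution. It rules out an exclusion that also drops same-day admissions, since day 0 belongs to the outcome period. It also means that the excluded share has to be checked at 65. For the same reason it would be too strong to say that these patients cannot receive CO@h; almost none would is as far as the documents go.

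**The SAP argues against exclusion.** It rejects dropping patients enrolled through A&E, because comparable patients who were never enrolled would stay in. That reasoning concerns exclusion by enrolment. It does not reach a rule based on admission status before the index date, applied on both sides of 65. The SAP also chooses the test date so as to evaluate the programme as used in practice, which makes an unrestricted analysis worth reporting.

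**Timing of outcomes.** A reader might infer that an inpatient's stay yields a critical care event but, by rule, no emergency admission. The SAP does not say whether an admission must begin after the test, so this is an ambiguity and not a demonstrated mismatch.

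**Conclusion.** The gap is real: nothing in the SAP removes or separately handles patients admitted before their first positive test. Its consequence is lost precision, not bias. That conclusion assumes that the inpatients' share and risk do not jump at 65. The size depends on f, which the documents do not give. Required N is 1.28, 1.74 or 2.63 times the Table 1 figure at f = 20%, 40% or 60%, and ICU is the more exposed outcome because its community rate is so low. The direction does not depend on the assumed values, provided inpatients carry the higher event risk. The change is worth making because the study already expects to be short of power on these outcomes.

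**What to change.** Record the following in the SAP or its planned addendum before outcomes are analysed:

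- Using HES, exclude patients whose admission began before the index date and who were still in hospital on it. Apply the rule on both sides of 65, whatever the onboarding status.
- Keep patients admitted on the index date itself, and count that admission as a day-0 outcome.
- Report the number and share excluded on each side of 65, and test that share for a discontinuity at 65.
- Report the unrestricted cohort alongside. If the excluded share does jump at 65, treat the unrestricted cohort as the main analysis.

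The cost is one rule and one check on linked data already requested. The downside is the loss of a small number of patients onboarded on clinical diagnosis and then admitted before the test. The balance check and the unrestricted analysis would expose any effect of that loss.
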